16.3.2 Ethics Committee Approval

It is the responsibility of the CRO to submit this protocol, the informed consent documents (approved by FMD), relevant supporting information and all types of subject recruitment information to the relevant EC for review, and all must be approved prior to the start of subject screening. Advertisements must be approved by the EC prior to their use at the study site, if applicable. Prior to implementing changes in the study, FMD and the ECs must also approve any substantial amendments to the protocol and corresponding updates to the informed

consent documents. For non-substantial protocol amendments (that do not require EC approval) and subsequent updates of the informed consent documents, all changes will be done in agreement with FMD and the study sites.

The CRO is responsible for keeping the relevant EC apprised of the progress of the study and of any changes made to the protocol. FMD (or a nominated delegate) will keep the ECs informed of any serious and significant AEs.

16.4 Confidentiality

Data collected during this study may be used to support the development, registration or marketing of a medicinal product. FMD will control all data collected during the study, and will abide by the General Data Protection Regulation (GDPR) (EU) 2016/679 concerning the processing and use of subjects' personal data. For the purpose of GDPR, FMD will be the data controller.

After subjects have consented to take part in the study, their medical records and the data collected during the study will be reviewed by FMD and/or its representatives. These records and data may, in addition, be reviewed by the following: independent auditors who validate the data on behalf of FMD, national or local Regulatory Authorities, and the ECs which gave approval for this study to proceed.

Subjects will be known by a unique subject number. The results of this study containing the unique subject number and relevant medical information including ethnicity may be recorded and transferred to and used in other countries throughout the world, which may not afford the same level of protection that applies within the EU and countries participating this study. The purpose of any such transfer would be to support regulatory submissions made by FMD in such countries.

16.5 Publication Policy

If the Sponsor, CRO and CI agree that it is desirable to publish the results of this study; all parties will liaise in good faith to publish the results. The CRO/CI agree to obtain the Sponsor's prior written approval of such publications.

18.1 IIEF Questionnaire

INTERNATIONAL INDEX
OF ERECTILE FUNCTION
(IIEF)

Subject Questionnaire

These questions ask about the effects that your erection problems have had on your sex life over the last four weeks. Please try to answer the questions as honestly and as clearly as you are able. In answering the questions, the following definitions apply:

- sexual activity includes intercourse, caressing, foreplay & masturbation
- sexual intercourse is defined as sexual penetration of your partner
- sexual stimulation includes situation such as foreplay, erotic pictures etc.
- ejaculation is the ejection of semen from the penis (or the feeling of this)
- orgasm is the fulfilment or climax following sexual stimulation or intercourse

Over the past 4 weeks:	Please check one box only
 Q1 How often were you able to get an erection during sexual activity?	0 No sexual activity 1 Almost never or never 2 A few times (less than half the time) 3 Sometimes (about half the time) 4 Most times (more than half the time) 5 Almost always or always
 Q2 When you had erections with sexual stimulation, how often were your erections hard enough for penetration?	0 No sexual activity 1 Almost never or never 2 A few times (less than half the time) 3 Sometimes (about half the time) 4 Most times (more than half the time) 5 Almost always or always
 Q3 When you attempted intercourse, how often were you able to penetrate (enter) your partner?	0 Did not attempt intercourse 1 Almost never or never 2 A few times (less than half the time) 3 Sometimes (about half the time) 4 Most times (more than half the time) 5 Almost always or always
 Q4 During sexual intercourse, how often were you able to maintain your erection after you had penetrated (entered) your partner?	0 Did not attempt intercourse 1 Almost never or never 2 A few times (less than half the time) 3 Sometimes (about half the time) 4 Most times (more than half the time) 5 Almost always or always
 Q5 During sexual intercourse, how difficult was it to maintain your erection to completion of intercourse?	0 Did not attempt intercourse 1 Extremely difficult 2 Very difficult 3 Difficult 4 Slightly difficult 5 Not difficult

- Q6 How many times have you attempted sexual intercourse?
 0 No attempts
 1 One to two attempts
 2 Three to four attempts
 3 Five to six attempts
 4 Seven to ten attempts
 5 Eleven or more attempts
- Q7 When you attempted sexual intercourse, how often was it satisfactory for you?
 0 Did not attempt intercourse
 1 Almost never or never
 2 A few times (less than half the time)
 3 Sometimes (about half the time)
 4 Most times (more than half the time)
 5 Almost always or always
- Q8 How much have you enjoyed sexual intercourse?
 0 No intercourse
 1 No enjoyment at all
 2 Not very enjoyable
 3 Fairly enjoyable
 4 Highly enjoyable
 5 Very highly enjoyable
- Q9 When you had sexual stimulation or intercourse, how often did you ejaculate?
 0 No sexual stimulation or intercourse
 1 Almost never or never
 2 A few times (less than half the time)
 3 Sometimes (about half the time)
 4 Most times (more than half the time)
 5 Almost always or always
- Q10 When you had sexual stimulation or intercourse, how often did you have the feeling of orgasm or climax?
 1 Almost never or never
 2 A few times (less than half the time)
 3 Sometimes (about half the time)
 4 Most times (more than half the time)
 5 Almost always or always
- Q11 How often have you felt sexual desire?
 1 Almost never or never
 2 A few times (less than half the time)
 3 Sometimes (about half the time)
 4 Most times (more than half the time)
 5 Almost always or always
- Q12 How would you rate your level of sexual desire?
 1 Very low or none at all
 2 Low
 3 Moderate
 4 High
 5 Very high
- Q13 How satisfied have you been with your overall sex life?
 1 Very dissatisfied
 2 Moderately dissatisfied
 3 Equally satisfied & dissatisfied
 4 Moderately satisfied
 5 Very satisfied
- Q14 How satisfied have you been with your sexual relationship with your partner?
 1 Very dissatisfied
 2 Moderately dissatisfied
 3 Equally satisfied & dissatisfied
 4 Moderately satisfied
 5 Very satisfied
- Q15 How do you rate your confidence that you could get and keep an erection?
 1 Very low
 2 Low
 3 Moderate
 4 High
 5 Very high

18.2 SEP Questionnaire

Male Version

1. Sexual Encounter Profile Diary question number 1:
'Were you able to achieve at least some erection (some enlargement of the penis)?'
2. Sexual Encounter Profile Diary question number 2:
'Were you able insert your penis into your partner's vagina?'
3. Sexual Encounter Profile Diary question number 3:
'Did your erection last long enough for you to have successful intercourse?'
4. Sexual Encounter Profile Diary question number 4:
'Were you satisfied with the hardness of your erection?'
5. Sexual Encounter Profile Diary question number 5:
'Were you satisfied overall with this sexual experience?'

Female Version

1. Sexual Encounter Profile Diary question number 1:
'Was your partner able to achieve at least some erection (some enlargement of the penis)?'
2. Sexual Encounter Profile Diary question number 2:
'Was your partner able to insert his penis into your vagina?'
3. Sexual Encounter Profile Diary question number 3:
'Did your partner's erection last long enough for you to have successful intercourse?'
4. Sexual Encounter Profile Diary question number 4:
'Were you satisfied with the hardness of your partner's erection?'
5. Sexual Encounter Profile Diary question number 5:
'Were you satisfied overall with this sexual experience?'

18.3 SEAR Questionnaire

Male and Female Version

SEAR domains (subscales)	SEAR items (for women/men)
Sexual relationship domain	1. I felt relaxed about initiating sex with my partner.
	2. I felt confident that during sex my arousal/erection would last long enough.
	3. I was satisfied with my sexual performance.
	4. I felt that sex could be spontaneous.
	5. I was likely to initiate sex.
	6. I felt confident about performing sexually.
	7. I was satisfied with our sex life.
	8. My partner was unhappy with the quality of our sexual relations.
Confidence domain (Self-esteem subscale)	9. I had good self-esteem.
	10. I felt like a whole woman/man.
	11. I was inclined to feel that I am a failure.
Confidence domain (Overall relationship subscale)	12. I felt confident.
	13. My partner was satisfied with our relationship in general.
	14. I was satisfied with our relationship in general.

**Response options*

Almost always/always.

Most times (much more than half the time).

Sometimes (about half the time).

A few times (much less than half the time).

Almost never/never.

Scoring

All questions except questions 8 and 11 were scored as 1=almost never/never, 2=a few times (much less than half the time), 3=sometimes (about half the time), 4=most times (much more than half the time), and 5=almost always/always. Questions 8 and 11 were reverse scored, with 5=almost never/never, 4=a few times (much less than half the time), 3=sometimes (about half the time), 2=most times (much more than half the time), and 1=almost always/always. Thus, a higher score signified a more favorable response for all 14 items.

Domain (Sexual Relationship, items 1–8; Confidence, items 9–14), subscale (Self-Esteem, items 9–12; Overall Relationship, items 13 and 14), and total scores (items 1–14) were computed by summing their respective items. Each domain score, subscale score, and overall (total) score was transformed onto a 0–100 scale: transformed score = $100 \times [(actual\ raw\ score - lowest\ possible\ raw\ score) / possible\ raw\ score\ range]$. Higher scores indicated a more favorable response (0=least favorable, 100=most favorable).

18.4 GAQ**Male Version**

1. GAQ question number 1:

'Has the treatment you have been taking improved your erectile function?'

2. GAQ question number 2:

'If yes, has the treatment improved your ability to engage in sexual activity?'

Female Version

1. GAQ question number 1:

'Has the treatment you have been taking improved your partner's erectile function?'

2. GAQ question number 2:

'If yes, has the treatment improved his ability to engage in sexual activity?'

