11.2 Efficacy Assessments

The efficacy of MED2005 will be assessed using the following subject-centred questionnaires at the time points described in the schedule of events ([Table 1](#)):

- The co-primary efficacy endpoints:
 - The IIEF-EF domain of the IIEF questionnaire, completed by the male subjects
 - Question 2 of the SEP questionnaire, completed by the male subjects
 - Question 3 of the SEP questionnaire, completed by the male subjects
- Secondary efficacy endpoints:
 - The SEAR questionnaire, completed by the male subjects and their female partners
 - Global assessment via completion of the GAQ, completed by the male subjects and their female partners
 - The additional domains of the IIEF questionnaire, completed by the male subjects
 - The other SEP questions (Questions 1, 4 and 5), completed by the male subjects
 - The SEP questions completed by the female partners
 - The PGI-S scale, completed by the male subjects
 - The PGI-C scale, completed by the male subjects
 - Time of onset and duration of action (erection) and erection hardness, completed by the male subjects and their female partners
 - Questions on the usage and application of the gels, completed by the male subjects

The IIEF, PGI-S, PGI-C and usage and application questions will be completed by the male subjects only. The SEP, SEAR, GAQ and time of onset and duration of action (erection) and erection hardness questions will be completed by both the subject and his female partner. For further details, please refer to [APPENDIX 1](#).

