- The change in the other domains of the IIEF questionnaire, the other SEP questions (Questions 1, 4 and 5), the overall SEAR questionnaire score, the scores in the two subdomains of the SEAR questionnaire (sexual relationship satisfaction and confidence) and the PGI-S at time points 4, 8 and 12 weeks will be analysed using ANCOVA as described for the primary endpoint analysis for SEP Questions 2 and 3. The PGI-C will be analysed using an analysis of variance (ANOVA)
- Subjective measures of the time of onset and duration of action (erection) and erection hardness will be analysed using Wilcoxon ranks for each intercourse attempt, averaged across intercourse attempts within each 4-week period for each subject. The averaged Wilcoxon rank data will be analysed using ANCOVA as described for the primary endpoint analysis

- Usage and application question responses will be summarised by treatment group

All efficacy assessments provided by the female partners will be analysed using the same statistical models as for the male subjects.

Open-label extension phase:

Summary statistics for all efficacy measures will be given for actual values and changes from baseline (where applicable), where the baseline assessments are the ones prior to the double-blind phase. Individual components of composite scores (but not domains) will not be summarised unless otherwise stated. Individual components as well as domains will be presented in listings together with the scores used in the analysis.

Summaries of responders at each Visit will be given using the same responder definitions as per the analysis of double-blind phase.

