18.6 Onset and Duration of Action (Erection) and Erection Hardness Questions

Male and Female Version

1. After application of the gel, when did you (and your partner) begin to notice your erection starting?

Please note: subjective measures of time will be used for all the following questions:

- Almost immediately.
 - Under 5 minutes.
 - Between 5 and 10 minutes.
 - Between 10 and 20 minutes.
 - Between 20 and 30 minutes.
 - Between 30 minutes and 1 hour.
 - Over 1 hour.
 - Not at all.
2. After application of the gel, when were you (and your partner) able to have penetrative sex?
 - Almost immediately.
 - Under 5 minutes.
 - Between 5 and 10 minutes.
 - Between 10 and 20 minutes.
 - Between 20 and 30 minutes.
 - Between 30 minutes and 1 hour.
 - Over 1 hour.
 - Not at all.
 3. From the time you began to notice your (your partner's) erection starting, how long did it last (estimated minutes)?
 - Under 5 minutes.
 - Between 5 and 10 minutes.
 - Between 10 and 20 minutes.
 - Between 20 and 30 minutes.
 - Between 30 minutes and 1 hour.
 - Over 1 hour.
 - Not at all.
 4. How would you rate the hardness of your (your partner's) erection during your sexual encounter?
 - 0 No enlargement
 - 1 Penis was larger, but not hard
 - 2 Penis was hard, but not hard enough for penetration
 - 3 Penis was hard enough for penetration, but not completely hard
 - 4 Penis was completely hard and fully rigid

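### Two partner-completed items in Appendix 1, female GAQ Question 1 and onset item 1, are misworded for a female respondent

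*Protocol*

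**What the plan says.** **Who answers.** Protocol section 11.2 lists among the secondary endpoints "Global assessment via completion of the GAQ, completed by the male subjects and their female partners". It assigns the onset, duration and hardness questions to both members of the couple as well. Partners complete the GAQ at Weeks 4, 8 and 12 (section 11.2.4), at home if they prefer (section 11.1.3). They answer the onset set at home after each intercourse attempt.

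**What the items ask.** The female GAQ in section 18.4 has two questions. Question 1 opens "Has the treatment you have been taking improved your partner" and ends by naming his erectile function. Question 2, put to those who answered yes, asks "has the treatment improved his ability to engage in sexual activity". Section 18.6 is a single text headed as serving men and women. Its item 1 asks "when did you (and your partner) begin to notice your erection starting".

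**How the answers are used.** Section 14.5.4 states: "All efficacy assessments provided by the female partners will be analysed using the same statistical models as for the male subjects". The GAQ goes into a logistic regression. The onset, duration and hardness answers are ranked, averaged within each 4-week period and analysed by ANCOVA. Both analyses come under the heading that the protocol describes as more exploratory.

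**The concern.** The gel goes on the man's glans penis, whether he or his partner applies it (section 8.2.4), so the treatment is his. Female GAQ Question 1 nevertheless speaks of a treatment that the woman herself takes. Onset item 1, put to the same woman, asks about an erection that is grammatically hers.

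These are texts given to respondents, and the answers are modelled as efficacy data. If a woman hesitates over what is meant, or reads either item literally, her answer carries error that has nothing to do with the man's response. An analysis plan cannot recover afterwards what a respondent understood. What is at stake is the quality of the partner GAQ and partner onset results.

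**Working it through.** No arithmetic bears on this point beyond a count of items. The check sets the partner-completed items in Appendix 1 beside each other and beside the stated intent.

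**Step 1: the GAQ.** The male Question 1 asks about the treatment the respondent has been taking and about his own erectile function. The female Question 1 converts the second half to the partner's erectile function and leaves the first half as it stands for the man. Female Question 2 is fully converted: "has the treatment improved his ability to engage in sexual activity". Since the next question refers to the man throughout, the clause in Question 1 looks like an incomplete conversion and not a choice.

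**Step 2: the onset, duration and hardness set.** Section 11.2.6 says that respondents are asked about their own or their partner's erection. Against that intent:

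| Item | Printed wording | Usable by the woman as printed? |
|---|---|---|
| 1 | "when did you (and your partner) begin to notice your erection starting" | No. The erection is the respondent's, with no alternative |
| 2 | "After application of the gel, when were you (and your partner) able to have penetrative sex" | Yes. It concerns an event shared by the couple |
| 3 | opens "From the time you began to notice your (your partner" and continues in the possessive | Yes. The alternative is printed |
| 4 | opens "How would you rate the hardness of your (your partner" and continues in the possessive | Yes. The alternative is printed |

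Item 1 departs both from items 3 and 4 and from section 11.2.6.

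**Step 3: the rest of the partner material.** The female SEP (section 18.2) is a separate version with all five questions converted. The SEAR (section 18.3) gives women/men alternatives where they are needed.

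| Questionnaire | Items the partner answers | Misworded for her |
|---|---|---|
| GAQ | 2 | 1 |
| Onset, duration, hardness | 4 | 1 |
| SEP | 5 | 0 |
| SEAR | 14 | 0 |
| Total | 2 + 4 + 5 + 14 = 25 | 2 |

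**Step 4: how an error would travel.** GAQ Question 2 depends on a yes to Question 1, so a mistaken no would also remove her Question 2 answer. In the onset set, a woman who took item 1 literally could choose the last category, which says that no erection was noticed. That answer would then enter her averaged rank. Both routes are possible. The protocol gives no rate for either.

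**Step 5: reach.** The three co-primary endpoints are assessed in the male subjects only (section 14.5.3). No success criterion uses partner answers.

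**The case against.** The strongest reply is that the meaning is plain in context. The study has one treatment. Female GAQ Question 1 names the partner's erectile function as the thing to be rated, and Question 2 goes on about him. Section 8.1 provides for partner training in the questionnaires and in gel application at Visit 1, and she may apply the gel herself. Most women will probably understand what is wanted. This stands in large part: on the GAQ the answer is still her rating of his function, and only the reference to whose treatment it is has gone astray. It does not make the text right. Training may reduce misreading but does not correct the item, and partners may answer away from the site. For onset item 1 the object itself, whose erection, is wrong for her.

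Three stronger readings are tempting and are not supported.

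- **That the partner questionnaires as a whole are written for the man.** The count above shows two items of 25.
- **That the GAQ difference between drug and placebo shrinks by a known amount.** If a share m of women in every arm answered no because they take nothing, the difference in yes rates would be multiplied by (1 − m). The protocol gives neither m nor an expected difference. Nothing in it shows that women would answer this way, and m could be near zero. The factor also requires misreading to be unrelated to arm and to the man's response.
- **That the joint phrasing in onset items 1 and 2 defeats independent corroboration of the man's report.** The protocol lists and models partner answers but nowhere says that they corroborate his independently. Item 2 works for either person as it stands.

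**Conclusion.** Two items are wrong for the person who is asked to answer them. One keeps the man's clause about treatment. The other asks a woman about her own erection, against the protocol's own description of the question. The consequence is avoidable response error of unknown size in the partner GAQ and partner onset outcomes, which are secondary and exploratory. The co-primary endpoints and the criteria for efficacy are unaffected. The point is minor, but worth correcting because the answers are modelled as efficacy data and the correction is small.

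The conclusion assumes that the text in Appendix 1 is what the ePRO displays and what is translated. The protocol does not show the ePRO screens. If the deployed versions are already correct, only the appendix needs to be brought into line.

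**What to change.** Change two items in Appendix 1 and in whatever is derived from it:

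- **Section 18.4, female GAQ Question 1:** make the treatment the partner's, for example *Has the treatment your partner has been taking improved his erectile function?*
- **Section 18.6, item 1:** insert *(your partner's)* before the word erection, as items 3 and 4 already do.

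Leave onset item 2, the male GAQ and the wording of item 1 as the man reads it unchanged. They have no demonstrated fault for their respondents.

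The cost is an update of two items in the ePRO and its translations, with any approval the amendment needs under section 16.3.2. No visit, subject or analysis is added.

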18.5 PGI Scales**PGI-S (Severity) Scale**

Please choose the response below that best describes the severity of your erectile dysfunction over the past 4 weeks.

1. None.
2. Mild.
3. Moderate.
4. Severe.
5. Very severe.

PGI-C (Change) Scale

Please choose the response below that best describes the overall change in your erectile dysfunction since you started using the study treatment.

1. Very much better.
2. Moderately better.
3. A little better.
4. No change.
5. A little worse.
6. Moderately worse.
7. Very much worse.

18.6 Onset and Duration of Action (Erection) and Erection Hardness Questions

Male and Female Version

1. After application of the gel, when did you (and your partner) begin to notice your erection starting?

Please note: subjective measures of time will be used for all the following questions:

- Almost immediately.
 - Under 5 minutes.
 - Between 5 and 10 minutes.
 - Between 10 and 20 minutes.
 - Between 20 and 30 minutes.
 - Between 30 minutes and 1 hour.
 - Over 1 hour.
 - Not at all.
2. After application of the gel, when were you (and your partner) able to have penetrative sex?
 - Almost immediately.
 - Under 5 minutes.
 - Between 5 and 10 minutes.
 - Between 10 and 20 minutes.
 - Between 20 and 30 minutes.
 - Between 30 minutes and 1 hour.
 - Over 1 hour.
 - Not at all.
 3. From the time you began to notice your (your partner's) erection starting, how long did it last (estimated minutes)?
 - Under 5 minutes.
 - Between 5 and 10 minutes.
 - Between 10 and 20 minutes.
 - Between 20 and 30 minutes.
 - Between 30 minutes and 1 hour.
 - Over 1 hour.
 - Not at all.
 4. How would you rate the hardness of your (your partner's) erection during your sexual encounter?
 - 0 No enlargement
 - 1 Penis was larger, but not hard
 - 2 Penis was hard, but not hard enough for penetration
 - 3 Penis was hard enough for penetration, but not completely hard
 - 4 Penis was completely hard and fully rigid

